**Table 6 Study groups, sub-cohorts, interventions, and blinding foreseen in the study: Stage B**

Stage B will only start after the last participant is randomized in Stage A.

Study groups	Number of maternal participants	Age of maternal participant at enrolment (Min/Max)	Intervention name	Study groups for randomization (Allocation 2:1)	Blinding		
					Maternal participants Only (Screening)	Maternal participants V1-C1 Infant participants V1-NB – V4NB (double-blind)	Infant participants only Contact 2-NB – V5-NB (double blind)
RSV_MAT	~3600	18 – 49 years	RSV_MAT	RSV_MAT	•	•	•
Control	~1800	18 – 49 years	Control	Control	•	•	•

## 4.2. Scientific rationale for study design

### 4.2.1. Study population

The study population mirrors that of the intended indication: pregnant women between 240/7 and 340/7 weeks gestational age (inclusive).

### 4.2.2. Use of placebo

The placebo group serves as a control for safety, reactogenicity, immunogenicity and efficacy assessments. No licensed vaccine against RSV is currently available.

### 4.2.3. Randomization ratio

A 2:1 randomization ratio was chosen to permit efficient evaluation of vaccine safety and efficacy without compromising statistical rigor. Ratios greater than 1:1 for vaccinated vs. placebo recipients increase the likelihood that reported events may occur among vaccine recipients. It is possible that a higher number of reported events among vaccine recipients may be attributed to the greater randomization ratio, the vaccine itself, or due to chance. GSK plans to mitigate the potential risk associated with the increased randomization of vaccinated to placebo participants by: a) improving standardization of reporting of predefined pregnancy related and neonatal AESI using GAIA definitions; b) conducting both epidemiological database studies and observational natural history studies to determine background rates for these events in different countries; and c) establishing processes for continuous review of blinded safety data by the SRT\* and unblinded safety data by the IDMC.

*\* Due to the safety signal observed, the study was fully unblinded to ensure the safety of the participants.*

### 4.2.4. Sub-cohorts

#### 4.2.4.1. Safety assessment in maternal participants

Assessment of vaccine reactogenicity (solicited events) in the 7 days post dose has been limited to Stage A to reduce the burden for maternal participants while ensuring enough observations to support robust evaluation.

#### 4.2.4.2. Blood sampling and immune response assessment (*Amended 23 February 2023*)

A sub-cohort for maternal blood sampling and assessment (immune response at Day 1 (Visit 1), Day 31 (Visit 2), and Delivery) has been defined to limit discomfort and risk while ensuring enough observations to support robust evaluation of secondary maternal immunogenicity objectives (see also [Table 3](#)).

Sub-cohorts for infant blood sampling have been defined to limit discomfort and risk while ensuring enough observations to support robust evaluation of immune response in maternal – infant pairs.

Note however that blood samples for assessment of immune response at Day 1 (Visit 1), Day 31 (Visit 2), and delivery (Visit 3) will be collected from *all* maternal participants. Cord blood will also be collected from all participants. These samples may also be tested to support possible safety assessments, if necessary.

***Note: In the immunogenicity sub-cohort, only those samples for which a pair (both maternal and respective infant) exist will be analyzed to evaluate secondary immunogenicity objectives and to assess antibody persistence in infants.***

**4.2.5. Adaptive design**

This adaptive trial design will provide evidence for the efficacy of the RSV maternal vaccine in the prevention of medically assessed, RSV-associated LRTI of any severity and medically assessed, RSV-associated severe LRTI. The design has 90% power to detect the target vaccine efficacies of 70% and 50% on severe and any-severity LRTI, respectively. If the vaccine meets these target VE estimates, this design offers the opportunity to identify this benefit with an expected sample size of approximately 7598 maternal participants, which may obviate the need to enroll the maximum sample size of 10 000.

Additional details are provided in Section 9.

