## 1.2. Schema

This is a multi-center, randomized, double-blinded, placebo-controlled study. Maternal participants 18 to 49 years of age (inclusive, at the time of the study intervention) will be assigned to one of 2 study groups and will receive a single intramuscular injection between 240/7 to 340/7 weeks of gestation (inclusive).

Up to approximately 10 000 participants will be enrolled; it is expected that at least 20% of these participants will be enrolled at centers located in the U.S.

Enrollment will occur in 2 sequential stages, A and B.

In Stage A, approximately 4600 maternal participants will be enrolled as follows:

- RSV Maternal (RSVPreF3) vaccine, 120 µg (N ~ 3067),
- Control (Lyophilized sucrose placebo; N ~ 1533).

In Stage B, an additional approximately 5,400 maternal participants will be enrolled:

- RSV Maternal (RSVPreF3) vaccine, 120 µg (N ~ 3600),
- Control (Lyophilized sucrose placebo; N ~ 1800).

During both stages, maternal participants who receive the study intervention will be followed for safety for up to approximately 10 to 11 months (from screening until 6 months after delivery). Infant participants will be evaluated for the occurrence of medically assessed, RSV-associated lower respiratory tract *illnesses* and safety for 12 months after birth.

In addition, during Stage A:

- All maternal participants will be evaluated for reactogenicity;
- A sub-cohort of approximately 1533 maternal participants will be evaluated for immune response, including maternal – infant RSV-specific antibody transfer (approximately 1020 study vaccine recipients; approximately 510 control recipients);
- Sub-cohorts of infant participants whose mothers were in the immunogenicity sub-cohort referred to above, will be evaluated for RSV-specific antibody levels post-birth (in total, approximately 1020 infants born to vaccine recipients evaluated for immune response and approximately 510 infants born to control recipients evaluated for immune response).

***Note: In the immunogenicity sub-cohort, only those samples for which a pair (both maternal and respective infant) exist will be analyzed to evaluate secondary immunogenicity objectives, since sample collection in infants was discontinued following stop of enrollment.***

Section 4.1 provides an overview of the study design.

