**9. STATISTICAL CONSIDERATIONS****9.1. Statistical hypotheses**

There are no hypotheses test for vaccine efficacy endpoints.

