**9.2. Sample size determination**

Note: A total of 5328 participants have been enrolled and vaccinated in the study so far, and there will be no new maternal participants vaccinated. Please refer to Section 2.3 for details. However, monitoring will continue for rest of the study period. All planned objectives will be assessed for the participants enrolled so far.

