### **9.5. Interim analyses**

Interim analyses may be performed, if deemed required.

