8. CHANGES FROM PLANNED ANALYSES

- By-participant listings of SAEs, AEs leading to study withdrawal, MAEs, adverse pregnancy outcomes and pregnancy related AESIs will be prepared and released. Such listings have already been released in earlier analyses. Due to study enrolment/vaccination stop, the study has been unblinded already before the final analysis.
- A sensitivity analysis for immunogenicity results excluding participants from Bangladesh, for which HIV testing was not performed before their enrollment into the study, has been added.
- Between group evaluations for immunogenicity analysis was clarified to be performed among RSV MAT and Control instead of vaccination groups, the wording has been corrected.
- In February 2022, enrollment and vaccination were stopped because of an imbalance in preterm births and associated neonatal deaths observed between the RSVPreF3-Mat and placebo groups. Subsequently the study was unblinded, and therefore the presented VE endpoints are descriptive.
- Subgroup analyses by economic region (LMIC and HIC) will be performed for demography, efficacy, and safety evaluations.
- Subgroup analyses by gestational age at birth will be performed for demography and safety evaluations.
- Sensitivity analysis for primary efficacy endpoints by using a negative binominal regression model have been removed.

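### Does Protocol 4.2.5 need changing because it still states 90% power and about 7598 women after vaccination stopped at 5328?

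*Protocol*

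**What the plan says.** Protocol 4.2.5, under the scientific rationale for the design, states: "The design has 90% power to detect the target vaccine efficacies of 70% and 50% on severe and any-severity LRTI, respectively". It adds that, at those target efficacies, benefit could be identified with "an expected sample size of approximately 7598 maternal participants, which may obviate the need to enroll the maximum sample size of 10 000". It closes with "Additional details are provided in Section 9" and carries no note about the stop.

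The current statistical text reads differently:

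- Protocol 9.1: "There are no hypotheses test for vaccine efficacy endpoints".
- Protocol 9.2: "A total of 5328 participants have been enrolled and vaccinated in the study so far, and there will be no new maternal participants vaccinated".
- Protocol 9.5: "Interim analyses may be performed, if deemed required". Protocol 9.5.2 and SAP 7.2 are both marked not applicable.
- SAP section 8: "Subsequently the study was unblinded, and therefore the presented VE endpoints are descriptive".

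The stop is also given in Protocol 1.1 and 2.3, and 10.6.4 dates it to 25 February 2022. The planning sizes remain elsewhere as upper limits. Protocol 1.2 has "Up to approximately 10 000 participants will be enrolled", and similar limits stand in Protocol 6.3.2.1 and 6.3.2.1.2 and in SAP section 3 and Table 3.

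**The concern.** Section 4.2.5 is live protocol text in the present tense, not an amendment log. It credits the study with a power figure, an expected size and a route to early success, and it names Section 9 as the source of detail. Section 9 no longer holds any of these.

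Power belongs to a test, so with no VE hypothesis the 90% cannot describe the trial now being run, and 7598 women can no longer be reached. With the operating-characteristics appendix redacted, this is also the only readable power statement in the current text. Someone taking the design description from it could present descriptive VE from a stopped trial as if it came from a study powered at 90%.

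**Working it through.** **Planned size against delivered size.** Inputs are 7598 and 10 000 (Protocol 4.2.5), 5328 (9.2), planned arms of 3067 + 3600 = 6667 vaccine and 1533 + 1800 = 3333 control (1.2), and 3557 vaccine recipients (2.3).

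- 5328 / 7598 = 0.701, a difference of 2270.
- 5328 / 10 000 = 0.533, a difference of 4672.
- Control recipients: 5328 − 3557 = 1771.
- By arm: 3557 / 6667 = 0.534 and 1771 / 3333 = 0.531, so the 2:1 split was kept.

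These are shares of an expectation and of a ceiling. They do not measure a missed target.

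**Can the 90% be reproduced?** Not exactly: alpha, its split across endpoints and looks, the VE method and the interim rules are not visible. The 7598 is an average over early stopping and needs those rules, so it cannot be checked either. What can be checked is whether 90% is plausible at the maximum size.

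Inputs for that check:

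- Allocation 2:1 and VE of 70% (severe) and 50% (any severity), from the current text.
- Control attack rates of 1% (severe) and 3% (any severity), the base case in the Protocol's list of tables.
- Success if VE exceeds 20% on either endpoint. This is the superseded criterion, shown in the amendment history and used only to test the planning figure.
- Assumed one-sided alpha of 0.025 or 0.0125.

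For a single endpoint, with p1 = p0(1 − VE):

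SE = √[(1 − p1)/(n_v·p1) + (1 − p0)/(n_c·p0)]

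Power = Φ{[ln(0.8) − ln(1 − VE)]/SE − z(1 − α)}

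Severe, N = 10 000, α = 0.025: SE = √(0.997/20 + 0.99/33.33) = 0.282, and 0.981/0.282 − 1.960 = 1.518, so power is 0.935.

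Any severity, same N and α: SE = √(0.985/100 + 0.97/100) = 0.140, and 0.470/0.1398 − 1.960 = 1.40, so power is 0.919.

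The other results come from the same formula, from an exact conditional binomial averaged over Poisson event counts, and from a simulation of success on either endpoint with severe cases nested in all cases. Each cell gives α = 0.025 / 0.0125.

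| N | Severe, log / exact | Any severity, log / exact | Either, no loss | Either, 10% loss |
|---|---|---|---|---|
| 10 000 | 0.935, 0.892 / 0.922, 0.873 | 0.919, 0.869 / 0.896, 0.837 | 0.971 / 0.944 | 0.955 / 0.918 |
| 5328 | 0.719, 0.617 / 0.677, 0.548 | 0.689, 0.584 / 0.637, 0.532 | 0.807 / 0.700 | 0.762 / 0.646 |

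In each of the middle two columns the first pair is the log approximation and the second pair the exact calculation.

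So 90% is a reasonable planning figure for the full design. At 5328 the former criterion would have given about 65% to 81% for either endpoint. That range is sensitive to the attack rate: with 5235 infants and α = 0.0125, success on either endpoint is about 37% at half the base rates, 69% at the base rates and 95% at double. None of these is a current power, because no test remains.

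**The other planning sizes.** The 10 000 and 5400 are worded as upper limits. SAP section 3 gives a range of 4600 to 10 000, and 5328 lies inside it. These figures are not false.

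**The case for a change.** The strongest case for a change is that the sponsor added post-stop notes to the text around 4.2.5 (4.2.3, 4.2.4.2 and Table 9) and left 4.2.5 untouched. The present tense does not tell the reader that a past plan is being described, and the notes elsewhere do not withdraw the 90% or the 7598. The month 6 and month 12 results are due for public disclosure and the latter for a study report (SAP 7.1), so a wrong power claim could be carried forward. A one-line note would cost almost nothing.

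The first part stands: the paragraph was overlooked and a note would be tidier. The rest does not carry. The paragraph sits under the design rationale and speaks of what the design can do, not of the women enrolled. Its only cross-reference leads to 9.1 and 9.2, which remove the test and give the final size. To be misled, a reader must ignore that reference, the note in 1.1, the account in 2.3 and SAP section 8. No document proposes to cite 90% power for the results.

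**Conclusion.** No change to the plan is needed. Protocol 4.2.5 is stale by oversight: it describes the pre-stop design without saying so, and the delivered size is 70.1% of the expected 7598. The current position is stated where it governs the analysis. There is no VE test, vaccination is closed at 5328 women, and VE is descriptive. The 90% is consistent with the full design under the listed attack rates and is used for nothing now, so marking it as superseded would alter no estimate, interval, analysis set or procedure. A replacement power would be worse than none, since it would attach a figure to a test that does not exist and would swing widely with the attack rate.

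The plausibility check assumes the superseded 20% criterion, one-sided alpha of 0.0125 to 0.025 and loss of 0% to 10%. The conclusion that no change follows does not depend on it; it rests on 9.1, 9.2 and SAP section 8.

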**4.2.6. Case definitions**

Cases will be classified (during data analyses) according to the definitions that follow. Case definitions should not be confused with the definitions study personnel use during RTI surveillance (Section 8.4).

**4.2.6.1. Maternal, medically attended respiratory tract illness (MA-RTI)**

**Table 7 MA-RTI case definitions for data analysis in maternal participants**

RSV-MA-RTI	Medically attended visit for RTI symptoms AND Confirmed RSV infection 
RSV hospitalization	Confirmed RSV infection AND Hospitalized for acute medical condition 
All-cause MA-RTI	Medically attended visit for RTI symptoms

 Confirmed RSV infection defined in Section 4.2.6.3

 RSV (nasal swab) sampling and testing as specified in Table 12.

 Hospitalization is defined as admission for observation or treatment based on the judgement of a health care provider.

**4.2.6.2. Respiratory tract illness (RTI) / Lower respiratory tract illness (LRTI) in infants****Table 8 RTI/LRTI case definitions for data analysis in infants**

RSV-RTI	Runny nose, OR Blocked nose, OR Cough AND Confirmed RSV infection 
RSV-LRTI	History of cough OR difficulty in breathing  AND SpO 2 < 95%  , OR RR increase  AND Confirmed RSV infection 
RSV-severe LRTI	Meeting the case definition of RSV-LRTI AND SpO 2 < 93%  , OR lower chest wall in-drawing OR inability to feed OR failure to respond / unconscious
RSV hospitalization	Confirmed RSV infection  AND Hospitalized for acute medical condition 
All-cause RTI	Runny nose, OR Blocked nose, OR Cough
All-cause LRTI	History of cough OR difficulty in breathing  AND SpO 2 < 95%  , OR RR increase 
All-cause LRTI hospitalization	Hospitalized due to all cause LRTI as defined above

Definitions based on [Modjarrad, 2016] except that definitions for severe and very severe RSV LRTI have been merged. RTI = respiratory tract illness; LRTI = lower respiratory tract illness; RR = respiratory rate; SpO2 = blood oxygen saturation by pulse oximetry.

Based on history reported by parents/LARs and includes difficulty in breathing (e.g. showing signs of wheezing or stridor, tachypnoea, flaring [of nostrils], chest in-drawing, apnea).

 For blood oxygen saturation (SpO2), the lowest value monitored will be used. In high altitudes (>2500m), SpO2 <92% for LRTI, <90% for severe LRTI.

 RR increase defined as:

> 60/minute (< 2 months of age)

> 50/minute (2 to < 12 months of age)

> 40/minute (12 to 24 months of age)

 Confirmed RSV infection defined in Section 4.2.6.3

 RSV (nasal swab) sampling and testing as specified in Table 14.

 Hospitalization is defined as admission for observation or treatment based on the judgement of a health care provider.

**Table 9 Alternative LRTI / Severe LRTI case definitions for data analysis in infants**

To meet an alternative case definition, a participant must have at least one item from each column.

[figure not shown]
*Note: The alternative case definitions will no longer be considered for data analysis in infants.*

	RSV confirmed	Documented Physical Examination (PE) findings indicating lower respiratory tract involvement	Objective measures of clinical severity
LRTI	Confirmed RSV infection as defined in Section 4.2.6.3	Rhonchi Crackles (Rales) Wheeze	Increased respiratory rate (bpm) 
 
• ≥ 60 for < 2 mo
 
• ≥ 50 for 2-6 mo
 

			Hypoxemia: 
 
• SpO2 <95% at ≤1800 meters
 
• SpO2 <92% at > 1800 meters
 

			New onset apnea
			Nasal flaring
			Retractions
			Grunting
Severe LRTI	Confirmed RSV infection as defined in Section 4.2.6.3	Rhonchi Crackles (Rales) Wheeze	Hypoxemia 
 
• SpO2 <93% at ≤1800 meters
 
• SpO2 <90% at > 1800 meters
 

			Acute hypoxic or ventilatory failure
			Dehydration due to respiratory distress requiring nasogastric/IV hydration
			Failure to respond or unconscious

**4.2.6.3. RSV infection**

The sponsor will analyze nasal swabs by quantitative reverse transcription polymerase chain reaction (qRT-PCR) for the presence of RSV A/B. A positive (RSV A or B) test result constitutes a case of RSV infection. Refer to [Table 12](#), [Table 14](#) and Section 8.4.

In the event the collection of a nasal swab for testing by the sponsor is impossible, results from locally collected samples, tested with locally approved tests, may also be considered for the determination of a case of RSV infection.

### 4.3. Justification for dose

A single formulation of the investigational RSV maternal vaccine (containing 120µg of the RSVPreF3 antigen) is planned. Currently available data suggest that the 120 µg formulation has an acceptable safety profile and tends to elicit stronger immune responses in non-pregnant women (RSV MAT-001 and RSV MAT-011) and pregnant women (RSV MAT-004), which is likely to result in higher placental transfer of antibodies to the fetus than formulations containing 30 or 60 µg of the RSVPreF3 antigen. Available results from these studies are included in the Investigator Brochure.

Because re-infection with RSV occurs throughout an individual's lifetime, it is extremely unlikely that an adult (in this case, a maternal participant) *would not* have been naturally infected with RSV before. Results of study RSV MAT-001 in non-pregnant women indicate that a single dose of the study vaccine is sufficient to boost the neutralizing antibodies induced by previous natural infections.

The study vaccine will be administered between 240/7 and 340/7 weeks of gestation (inclusive). This gestational age range is considered optimal for both immunogenicity and safety. It allows enough time to (a) induce high neutralizing antibody levels in maternal participants before delivery and (b) ensure these antibody levels are elevated during the period of greatest placental antibody transfer to the fetus. Moreover, it is after the critical period for organogenesis (i.e. after the period when most congenital abnormalities develop).

### 4.4. End of Study definition

A participant is considered to have completed the study if he/she returns for the last visit as described in the protocol.

The Primary Completion Date (PCD) occurs on completion of the Month 12 post-delivery visit (Contact 1 for the maternal participants and Visit 5-NB for the infant participants).

End of Study (EoS) occurs with the date of last (infant) participant last visit (LSLV) or the last testing/reading released of the human biological samples related to primary and secondary endpoints, whichever comes last. EoS must be achieved no later than 8 months after LSLV.

## 5. STUDY POPULATION

### 5.1. Inclusion criteria for enrolment

Adherence to these criteria as specified in the protocol is essential. Inclusion criteria deviations are not allowed because they can jeopardize the scientific integrity or regulatory acceptability of the study or participant safety.

**5.1.1. Maternal participants**

Maternal participants must satisfy all the following criteria at study entry:

- Participants who, in the opinion of the investigator, can and will comply with the requirements of the protocol (e.g. completion of diaries, return for follow-up visits).
- Participants who give written or witnessed/thumb printed informed consent after the study has been explained according to local regulatory requirements, and before any study specific procedures are performed. The informed consent given at screening should (consistent with local regulations / guidelines) either:
  - include consent for both the maternal participant’s participation and participation of the infant after the infant’s birth, or
  - include consent for the maternal participant’s participation and expressed willingness to consider permitting the infant to take part after the infant’s birth (if local regulations/guidelines require parent(s) to provide an additional informed consent after the infant’s birth).
  - Both mother and father should consent if local regulations/guidelines require it.
- Age 18 to 49 years, inclusive, at the time of study intervention.
- Pre-pregnancy BMI (based on participant’s report) 17.0 to 39.9 kg/m^2, inclusive.
- In good general maternal health as established by medical history and clinical examination before entering into the study.
- Singleton pregnancy (including instances where the singleton pregnancy derives from a vanishing twin syndrome).
- At 240/7 to 340/7 weeks of gestation at the time of study vaccination (Visit 1), as established by:
  - Last menstrual period (LMP) date corroborated by first or second trimester ultrasound examination (U/S) i.e. at or before 28 weeks of gestation.
  - 1st or 2nd trimester U/S only, if LMP is unknown/uncertain
  - Certain LMP, corroborated by an U/S performed after 28 weeks of gestation is also acceptable.

NOTES: If pregnancy resulted from assisted reproductive technologies, LMP date may be replaced by IUI (intrauterine insemination) or ET (embryo-transfer) date.

If LMP (or IUI or ET) and U/S performed before 28 weeks of gestation, do not correlate, default to U/S gestational age assessment.

If the first U/S is only performed after 28 weeks of gestation (i.e. 3rd trimester) and there is no other basis for estimating gestational age, or the only other basis is fundal height, then the GA calculation is uncertain and the woman should be excluded.

The level of diagnostic certainty of the gestational age should be established by using the Global Alignment of Immunisation safety Assessment in pregnancy (GAIA) gestation age assessment tool (Section 10.8).

- No fetal genetic abnormalities (based on genetic testing, if performed).
- No significant congenital malformations (such as abnormal fetal morphology, abnormal amniotic fluid levels, significant abnormalities in placenta or umbilical cord), as assessed by fetal anomaly ultrasound scan (also known as a level 2 ultrasound or fetal morphology assessment) conducted at or beyond 18 weeks of gestation.
- Willing to provide cord blood.
- Who do not plan to give their child for adoption.
- Who plan to reside in the study area for at least one year after delivery.
- Willing to have the infant followed-up after delivery for a period of 12 months.

Note that women whose pregnancies resulted from Assisted Reproductive Technologies may be enrolled if they meet all inclusion criteria and none of the exclusion criteria.

